Study objectives	
Primary Objective
 
Absolute pain score 24h after surgery, assessed by 100mm visual analogue score (VAS).
 
Secondary Objectives
 
Minimal Clinically Important Difference [MCID] in visual analogue score; VAS adjusted for pain severity; postoperative morbidity; opioid use; heart rate variability [explanatory variable].

Study design	Phase II, single-centre, two-arm, parallel group randomised controlled trial
Setting	Surgical services of hospitals undertaking major trauma orthopaedic surgery.
Participants	
Inclusion criteria
 
 • Scheduled to undergo major elective or urgent (not requiring intervention in <24h) noncardiac (orthopaedic) surgery under general and/or spinal anaesthesia, expected to take >120 minutes from the induction of anaesthesia. • American society of Anaesthesiologists (ASA) grade I–III. • Aged 18 years and over. 
Exclusion criteria
 
 • Requiring invasive mechanical ventilation and/or new renal replacement therapy during hospitalization. • Cardiac arrhythmia requiring therapy prior to/during hospitalization. • Dementia. • Cancer requiring active/ongoing therapy. • Postural orthostatic tachycardia syndrome. • Lower limb neuromuscular disorders. • Auricular dermatitis. • Day-case surgery, not requiring overnight hospital admission.
Interventions	
Sham Group: Patients randomised to receive sham treatment will receive no current via the bilateral auricular leads for 50 minutes.
 
Stimulation Group: Patients randomised to receive stimulation will receive a sub-threshold current via the bilateral auricular leads for 50 minutes.

Primary outcome measure	The primary outcome is absolute pain score 24h after surgery, assessed using the 100mm visual analogue score.

Outcome measures

Primary outcome measure

The primary outcome will be the absolute VAS pain score 24h after surgery.

Secondary outcome measures

Minimally Clinical Important Difference: The proportion of participants who achieve a minimally clinical relevant reduction >10mm using the 100 mm pain Visual Analogue Score will be compared before and after the period of stimulation in each group, before and after surgery.[1]

VAS stratified by pain intensity: Absolute changes in pain score before and after sham/stimulation will be compared before and after the period of stimulation in each group before and after surgery, stratifying for mild, moderate, and severe pain intensity before the intervention. A pain VAS score of 30, 70, and 100 indicates the upper boundaries of mild, moderate, and severe pain intensity.[1]

Postoperative morbidity: Defined by the Post Operative Morbidity Survey (POMS) before (preoperative) and after (postoperative days 3 and 7) surgery. The POMS is an 18-item survey which examines nine domains (pulmonary, infection, renal, gastrointestinal, cardiovascular, neurological, haematological, wound, pain) of postoperative morbidity.[2] The POMS is a reliable and valid measure of short-term postoperative morbidity following major surgery.²⁰ The hospital electronic patient management system will be used to prospectively record POMS on postoperative days 0 (preoperative), 3 and 7. Clavien-Dindo grades for complications during hospital stay will also be reported.

Opiate use: Opiate consumption [expressed as morphine equivalents] before and for three days after surgery.

Explanatory measures

Autonomic function, as assessed by time and frequency domain measures of heart rate variability 10 minutes before and 10 minutes after each stimulation session, before and after surgery.[3]

Sample size and randomisation

Sample size calculation

Consensus perioperative guidelines recommend that the Visual Analogue Score should be used to assess pain intensity.[4] 72 patients are required to have a 90% chance of detecting, significant at the 1% level, a decrease in mean VAS (the primary outcome measure) from 34mm in the control group to 23mm in the experimental group after surgery (standard deviation of outcome 12mm). Allowing for 10% dropout per group, a final sample size of 86 participants is required, analysed by intention to treat.

Randomisation procedure

Randomisation will occur after the participant has provided informed consent before the surgical procedure is due to start. Participants are randomly assigned (1:1) by block randomisation to receive stimulation or sham stimulation to ensure a balance in sample size across groups over time (Power

Analysis & Sample Size (PASS) 2021, Utah, USA). Investigators will log on to a secure web-based randomisation file to obtain a unique patient identification number and allocation to a treatment group.

Analysis methods

General analysis principles

Analyses will follow the intention-to-treat principle: all randomised patients with a recorded outcome will be included in the analysis and analysed according to the treatment to which they were randomised [5, 6]. Patients will be included in the analysis, regardless of whether the treatment they received was compliant with the protocol. Definitions of what constitutes a recorded outcome for each outcome can be found in Appendix 1. Patients with missing outcome data will be excluded from the analysis. Missing data for baseline covariates to be included in the analysis model will be accounted for using mean imputation for continuous variables and the missing indicator approach will be used for missing data for categorical variables [7, 8].

For the analysis of the primary outcome, each secondary outcome, and all process measures, we will present the following information:

The number of patients included in each analysis, by treatment group

A summary statistic of the outcome (e.g. mean (SD), number (%)), by treatment group

The estimated treatment effect

A 95% confidence interval for the estimated treatment effect

A two-sided p-value

For all analyses, a significance level of 5% will be used.

Representativeness of patients

A log of eligible patients not recruited to the trial will be kept. Reasons for non-participation will be categorised and summarised. Participation in the trial, treatment allocation and completeness of follow-up will be illustrated by a CONSORT flow diagram [9].

Baseline characteristics

Baseline characteristics will be summarised for each treatment group by the mean and standard deviation or median and interquartile range for continuous variables, and the number and percent for categorical variables. The following baseline characteristics will be summarised by treatment group:

- Demographic: age (years), gender (male/female)
- Co-morbid disease: Hypertension; Ischaemic heart disease; Cardiac failure; Cardiac valvular disease
- Stroke/TIA; Peripheral vascular disease; Diabetes mellitus, type I; Diabetes mellitus, type II ; COPD; Asthma
Smoker; Interstitial or other respiratory disease; Liver cirrhosis; GI pathology-other; Osteoarthritis;
Rheumatoid arthritis; Inflammatory disease; Active cancer; Previous cancer
- ASA grade

- Medications: Statin; Anticoagulant; Antiplatelet; Beta-blocker; Calcium channel antagonist; Heart rate limiting calcium channel antagonist; Doxazosin; Diuretic; Nitrate; Angiotensin converting enzyme inhibitors; Angiotensin II Receptor Blockers; Other hypertensives; Other heart failure Rx; Digoxin/anti-arrhythmic; Other Rx Asthma Rx; Opioids-oral; Opioids- parental; NSAIDs; Paracetamol' Steroids; Metformin; Insulin; Any other diabetic medication
- Pre-operative blood test results (within 1 week before surgery or most recent): Haemoglobin; Serum Albumin; Creatinine; white cell count; Neutrophil count; Lymphocyte count; CRP
- Anxiety: GAD-7 and Amsterdam preoperative anxiety score.

Analysis software

All analyses will be conducted in NCSS 2021 (NCSS 2021 Statistical Software (2021). NCSS, LLC. Kaysville, Utah, USA, ncss.com/software/ncss).

Analysis of primary outcome

Primary analysis

Difference in absolute pain score 24h after surgery, assessed by 100mm visual analogue score (VAS), under the ITT principle [10]. Repeat-measures ANOVA will be used to compare VAS before versus after stimulation/sham, with post hoc Tukey-Kramer testing.

Analysis of secondary outcomes

Minimally clinical relevant reduction before and 24h after surgery: The proportion of participants who achieve a minimally clinical relevant reduction >10mm using the 100 mm pain Visual Analogue Score will be compared before and after the period of stimulation in each group, before and after surgery.[1] Paired t-test will compare between sham and stimulation groups.

VAS stratified by pain intensity: Absolute changes in pain score before and after sham/stimulation will be compared before and after the period of stimulation in each group before and after surgery, stratifying for mild, moderate, and severe pain intensity before the intervention. Repeat-measures ANOVA will be used to compare VAS before versus after stimulation/sham, with post hoc Tukey-Kramer testing.

Postoperative morbidity: Absence of POMS will be compared between groups serially [time to become free of morbidity after surgery]. Individual POMS will be reported in a separate table but not tested formally.

Opiate use: Opiate consumption [expressed as morphine equivalents] will be presented before and for three days after surgery, between stimulation/sham, but not tested formally.

Explanatory measures

The effect of stimulation/sham on time and frequency domain measures of heart rate variability 10 minutes before and 10 minutes after each stimulation session, before and after surgery.[3] . Repeat-

measures ANOVA will be used (group: stimulation/sham X experimental timepoint X before/after surgery), with post hoc Tukey-Kramer testing.

Exploratory analyses

Exploratory analyses will be repeated to examine the relationship between autonomic parameters and achieving MCID, independent of group allocation to stimulation/sham.

Sensitivity analysis

The amount of missing primary outcome data is anticipated to be minimal but will be accounted for in a sensitivity analysis if missing data is greater than 5%.

Other analyses, data summaries and graphs

Clinical management

Clinical management for sham/stimulation groups will be summarised but not subjected to statistical testing. Numbers (%) and means (SD) or medians (IQR) will be provided separately for each group. The sham/stimulation groups will be compared for the following clinical management characteristics:

- Anaesthetic technique
- level of care on the first night after surgery

Process measures

Summary measures will be presented separately for each treatment group. All patients with recorded data will be included in the summary. Formal statistical analysis will not be performed. Duration of hospital stay after surgery (days) will be summarised using median (IQR).

Safety analyses

Adverse events and serious adverse events will be presented as a number (%) by treatment group. All patients with a recorded outcome will be included in the summary. In addition to this, 'other' adverse events will be reported separately if prevalence is more than 5% across all participants in the trial.

- Arrhythmia
- Headache
- Pain
- Skin irritation at the stimulation site
- Dizziness
- Other
- None

Protocol deviations

Numbers and percentages of protocol deviations will be reported. Protocol deviations will be reported as participants who stopped therapy either during the stimulation period, before and/or after surgery. Stimulation current, as applicable, will be reported to demonstrate variation in protocol parameters.

Complications within 30 days after surgery

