≥1 treatment deviation		
Current before		
Current after		
Other deviation		

Table 4: Primary and secondary outcomes.

Outcomes	Number of patients with available data and included in analysis - no. (%)		Summary measure		Treatment effect (95% CI)	P-value
	Sham (n=XX)	Stimulation (n=XX)	Sham	Stimulation		
Primary outcome						
VAS 24h after surgery						
Secondary outcomes						
MCID						
VAS before surgery						
VAS [pain intensity]						
Opiate use						

Table 5: PostOperative Morbidity survey: reported before surgery, 3 and 7 days after surgery.

Complication	Number of patients with available data - no. (%)		Summary measure	
	Sham (n=XX)	Stimulation (n=XX)	Sham	Stimulation
De novo requirement for supplemental oxygen.				
Respiratory support.				
Currently on antibiotics.				
Temperature >38°C/ blood cultures in last 24h.				
Oliguria (< 500 mL/day),				
Serum creatinine (>30% from baseline value)				
Unable to tolerate normal enteral diet				
Nausea/vomiting.				
Myocardial infarction or ischemia				
Hypotension (drug therapy/fluid >200 mL/h)				
Atrial or ventricular arrhythmia				
Pulmonary edema				

De novo focal neurological deficit				
Coma.				
Confusion/delirium.				
Wound dehiscence requiring surgical exploration				
Wound drainage/pus.				
Blood, platelets, fresh frozen plasma or cryoprecipitate.				
Surgical wound pain-parenteral opiates				
Regional anesthesia.				
Not mobilising alone				
None				

Table 6: Process measures

Process measures	Number of patients with available data - no. (%)		Summary measure	
	Sham (n=XX)	Stimulation (n=XX)	Sham	Stimulation
Re-admission to hospital within 30 days of surgery – no. (%)				
Duration of hospital stay after surgery (days) - Median (IQR)				
Number of patients admitted to a critical care unit - no. (%)				

Table 7: Adverse events

Adverse Events - no. (%)	Sham (n=XX)	Stimulaton (n=XX)
Patients with ≥ 1 adverse event		
Total number of adverse events		
Type of adverse events		
Arrhythmia ^a		
Headache		
Pain ^b		
Skin irritation at the stimulation site		
Dizziness		
Other		
None		

^a Defined as clinically detected arrhythmia during or after day of intervention.

^b Defined as localised pain to auricular region

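### Preoperative POMS is collected, but mislabelled as a postoperative day and given no baseline role in the comparison of freedom from morbidity; adjusting for it would be a nearly free gain in precision

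*SAP*

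**What the plan says.** The SAP describes the timing of POMS in three places.

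- Secondary outcome measures, definition: "Defined by the Post Operative Morbidity Survey (POMS) before (preoperative) and after (postoperative days 3 and 7) surgery".
- Same paragraph, recording schedule: "record POMS on postoperative days 0 (preoperative), 3 and 7".
- Appendix 3, title of Table 5: "PostOperative Morbidity survey: reported before surgery, 3 and 7 days after surgery".

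The analysis is in Analysis of secondary outcomes: "Absence of POMS will be compared between groups serially [time to become free of morbidity after surgery". The separate items are descriptive: "Individual POMS will be reported in a separate table but not tested formally". No model, test or covariate is named for the between-group comparison.

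Preoperative POMS is absent from the list under Baseline characteristics and from Table 1. It appears only in Table 5, alongside the day 3 and day 7 results. General analysis principles does expect some adjustment ("Missing data for baseline covariates to be included in the analysis model will be accounted for using mean imputation for continuous variables"), but the SAP names no covariate for any outcome.

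The population is broad: "Scheduled to undergo major elective or urgent (not requiring intervention in <24h) noncardiac (orthopaedic) surgery". Allocation is randomised: "Participants are randomly assigned (1:1) by block randomisation to receive stimulation or sham stimulation".

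**The concern.** Whether a patient is free of morbidity on day 3 or day 7 probably depends in part on whether they were free of it before surgery. In a trauma orthopaedic service that also takes elective cases, some patients may already be on antibiotics or parenteral opiates before surgery. Both are Table 5 items, and the intervention cannot have caused either if they predate it.

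The trial records this information and then assigns it no use. At stake are some power and some protection against chance imbalance, on an outcome for which General analysis principles calls for an effect estimate, a confidence interval and a p-value. The contradictory label adds a smaller problem: it numbers a baseline value in the same series as the two outcome assessments.

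**Working it through.** **The plan's own figure.** The SAP gives no rate, effect size or sample size for POMS, so there is no POMS figure to reproduce. Its only calculation is for the VAS: difference 34 − 23 = 11 mm, SD 12 mm, 1% level, 90% power. Two-sided, n per arm = 2 × (2.576 + 1.282)² × 12² / 11² = 35.4, rounded up to 36, or 72 in total. This reproduces the SAP's 72. The recruitment target of 86 gives 86 / 2 = 43 per arm, used below. How 86 was reached from 72 is a separate matter.

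**Chance imbalance.** If a proportion p has POMS morbidity before surgery, the SD of the between-arm difference in that proportion is √(2p(1 − p)/43).

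- p = 0.1: √(0.18/43) = 0.065
- p = 0.3: √(0.42/43) = 0.099
- p = 0.5: √(0.50/43) = 0.108

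A typical chance imbalance is therefore about 6 to 11 percentage points.

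**Power with and without the covariate.** All rates here are assumptions. The set-up is 43 per arm, a binary POMS-free outcome at one assessment, odds ratio 2.7 for stimulation, logistic regression with and without preoperative POMS, two-sided 5%, and 3,000 simulated trials per row.

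| POMS-free if free / morbid before surgery | Morbid before surgery | Power unadjusted | Power adjusted | Gain (points) |
|---|---|---|---|---|
| 60% / 40% | 10% | 54% | 54% | 0 |
| 60% / 40% | 30% | 55% | 56% | 1 |
| 60% / 20% | 10% | 51% | 54% | 3 |
| 60% / 20% | 30% | 47% | 54% | 7 |
| 60% / 20% | 50% | 44% | 54% | 10 |
| 70% / 10% | 50% | 26% | 38% | 12 |

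A repeat of three rows gave 46% v 53% (60%/20%, 30% morbid), 42% v 52% (60%/20%, 50% morbid) and 25% v 38% (70%/10%, 50% morbid). The last is a gain of 13 points.

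A separate set used a linear model, an odds ratio of 3 and rates of 70% / 30%. Power was 50% v 52%, 52% v 57% and 55% v 62% at 10%, 30% and 50% morbid before surgery, a gain of about 2 to 6 points before rounding.

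**Validity without the covariate.** Under no treatment effect, the unadjusted type I error in the linear-model set was 5.4%, 4.4% and 4.5% at those three prevalences. The adjusted figures were 5.6%, 4.6% and 5.3%. In the logistic set both analyses were at about 4 to 5%. The omission costs precision only.

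**Limits.** The simulations assume no dropout and test one binary assessment. The SAP plans a serial, time-to-free comparison, so the figures indicate the order of the gain and do not predict it.

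**The case against.** The strongest reply is that the unadjusted comparison is valid. Allocation is randomised, so preoperative morbidity is balanced in expectation. Adjustment is then a matter of efficiency, on a secondary outcome of a phase II trial sized only on the VAS. The absence of named covariates is also general and not peculiar to POMS. All of this stands, and it is why the point is minor. It does not remove the point: the value is already collected, using it costs almost nothing, and the choice is better fixed before the data are seen.

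A reader might infer from the day 0 label that the preoperative record enters the tested series, so that a patient free of POMS before surgery counts as recovered at time zero. The document does not support that. The analysis sentence restricts the endpoint to the period after surgery, and the bracket in the schedule, the definition just before it and the Table 5 title all identify the record as preoperative. The label is a slip of wording.

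Two further cautions also stand. First, the SAP describes sessions before as well as after surgery, and says only that the record is preoperative. If it follows the first session it is a post-treatment value and not a clean covariate. Second, the Table 5 row on mobilising is a doubtful example of pre-existing morbidity, because mobility is not among the nine POMS domains the SAP lists. It is not relied on here.

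**Conclusion.** The point holds as a minor improvement. The label contradicts itself, and the preoperative value has no stated baseline role in the comparison of freedom from POMS morbidity. The consequence is lost precision and exposure to chance imbalance, without bias and without inflation of the false-positive rate.

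The size cannot be derived from the SAP. Under the assumed rates the gain from adjustment runs from about 0 points of power, when preoperative morbidity predicts the outcome only weakly, to about 13 points, when half the patients are morbid before surgery and the gradient is steep. With low prevalence (10%) the gain was at most about 3 points even at the 60% / 20% gradient. The case for adjustment rests on preoperative morbidity being reasonably common and predictive. Both are plausible in a mixed elective and urgent population, but neither is documented.

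**What to change.** Changes to the SAP wording:

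1. In Secondary outcome measures, replace the day 0 label with *preoperative (baseline)*, and state that day 3 is the first outcome assessment.
2. State whether the preoperative record is made before the first stimulation or sham session.
3. If it is, include preoperative POMS (present/absent) as a covariate in the between-group comparisons at days 3 and 7, naming the model, or stratify the time-to-free comparison by it. If it is not, report the value descriptively and say so.
4. Add preoperative POMS to the baseline characteristics and Table 1.

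No new data are needed, and the missing-indicator rule in General analysis principles already covers a missing categorical covariate. The cost is one model parameter and, with logistic regression, a conditional odds ratio. A standardised risk difference can be reported beside it.

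### The sample-size figures of 72 patients, 10% dropout and 86 randomised do not agree: 72 with 10% dropout gives 80, and 86 from 72 implies about 16% loss

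*SAP*

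**What the plan says.** The SAP, under Sample size calculation, sizes the trial on mean VAS after surgery: "72 patients are required to have a 90% chance of detecting, significant at the 1% level", for a fall "from 34mm in the control group to 23mm in the experimental group after surgery", with a "standard deviation of outcome 12mm". The next step is "Allowing for 10% dropout per group, a final sample size of 86 participants is required, analysed by intention to treat".

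Nothing else stands between 72 and 86: no second attrition allowance, no inflation formula and no named test. The sizing paragraph does not say whether the 1% level is one- or two-sided. The general analysis principles list "A two-sided p-value" for every analysis. Allocation is 1:1 (Randomisation procedure).

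**The concern.** A dropout of 10% in each arm is 10% overall, so 72 should grow to about 80. The SAP arrives at 86. The difference of 6 patients is too large for rounding, so at least one of the three figures (72, 10%, 86) does not belong with the other two.

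The number evaluable matters here. Under the general analysis principles, patients with no recorded outcome are left out of the analysis, so power rests on those with a 24h VAS and not on the number randomised. As written, a reader cannot tell whether the plan needs 72 or 76 evaluable patients, or whether it allows for 10% or 16% loss. If 14 of the 86 had no outcome, 72 would remain: the stated requirement would be met while the stated dropout allowance was exceeded.

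**Working it through.** **Inputs, all from the SAP.** Difference 34 − 23 = 11 mm; SD 12 mm; power 90%; level 1%; allocation 1:1; dropout 10% per group; final total 86. Two-sidedness is taken from the general analysis principles.

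**Step 1: reproduce 72.** Normal approximation for two means:

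n per arm = 2 × SD² × (z₀.₉₉₅ + z₀.₉₀)² / difference² = 2 × 144 × (2.576 + 1.282)² / 121 = 35.4, rounded up to 36.

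36 × 2 = 72, as stated, with normal-approximation power of 90.5%. Other readings do not give 72: one-sided 1% gives 62, two-sided 5% gives 52 and one-sided 5% gives 42. So 72 is a two-sided 1% figure by the normal approximation.

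**Step 2: inflate 72 for 10% dropout.**

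- Dividing per arm: 36 / 0.9 = 40, so 80 in total.
- Dividing the total: 72 / 0.9 = 80.
- The cruder multiplication: 72 × 1.1 = 79.2, rounded up to 80.

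Every version gives 80. The stated 86 is 6 higher.

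**Step 3: what loss links 72 to 86?** 1 − 72/86 = 16.3%. As an add-on, 86/72 − 1 = 19.4%. The SAP states neither.

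**Step 4: power by two-sample t-test (noncentral t, two-sided 1%).**

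| Per arm | Total | Power | Per arm / 0.9, rounded up | Total randomised |
|---|---|---|---|---|
| 36 | 72 | 88.9% | 40 | 80 |
| 37 | 74 | 89.9% | 42 | 84 |
| 38 | 76 | 90.8% | 43 | 86 |
| 39 | 78 | 91.7% | 44 | 88 |

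By t-test, 90% power needs 38 per arm, and 38/0.9 = 42.2, rounded up to 43 per arm, is exactly 86. That is one coherent route.

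**Step 5: other routes to 86.** 77/0.9 = 85.6 (inflating a total of 77); 78 × 1.1 = 85.8; and 72 × 1.2 = 86.4, rounded down, if 10% per group was added up over two groups to 20%. The last is not a valid inflation, but the SAP's wording does not exclude it.

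**Step 6: what 86 delivers.** 86 × 0.9 = 77.4, so about 77 evaluable. That lies between 38 and 39 per arm, so t-test power at two-sided 1% is between 90.8% and 91.7%, or about 91%.

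**The case against.** The best defence is that nothing is lost. The discrepancy runs upwards, 86 covers the stated power after a 10% loss, and no estimate, test or analysis set changes. That stands, and it makes this a correction to the reporting of the sample size rather than a design flaw. It does not remove the contradiction, because no standard inflation of 72 by 10% gives 86.

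Two stronger readings are tempting, and the SAP supports neither.

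- A reader might infer that 72 is wrong because its t-test power is 88.9%. But 72 is a valid normal-approximation answer, the SAP does not claim a t-test calculation, and the gap of 1.1 points is a difference of method.
- A reader might infer that 86 can only have come from 76. Among equal-arm totals, 76 is the only one that reaches 86 when each arm is divided by 0.9 and rounded up. The SAP states no inflation formula, however, and Step 5 shows other ways to arrive at 86. Where 86 came from is therefore conjecture.

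**Conclusion.** The inconsistency is real and rests on the document's own figures: 72 evaluable with 10% dropout in each arm is 80, not 86, and 86 from 72 means a loss of about 16%. The documents do not show which of the three figures is the wrong one, and this point does not presume it.

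The size is 6 patients in the stated total, or about 6 percentage points in the loss allowed for. Planned power is not at risk, at about 91% with 10% loss from 86. The power figures assume a two-sided 1% level, a common SD of 12 mm, equal arms and a simple comparison of two means. The step from 72 to 80 needs only the 10% and 1:1 allocation.

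**What to change.** Keep 86 and restate the paragraph so that each figure follows from the one before. Two versions do this:

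- 76 evaluable patients (38 per arm) give 91% power by two-sample t-test at two-sided 1%; allowing for 10% dropout per arm, 43 per arm (86) will be randomised.
- 72 evaluable patients (36 per arm) give 90% power by the normal approximation at two-sided 1%; 86 will be randomised, which allows for about 16% loss.

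If 72 and 10% are the intended figures, the stated total should be 80. The sponsor should choose the version that matches the calculation actually done, and name the method, the sidedness and the inflation formula.

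The cost is a sentence or two. Enrolment is unchanged under the first two versions; giving 80 would lower the stated total by 6. The restated text would still carry the 1% level, while the general analysis principles set 5% for all analyses. That is a separate matter, but the same edit is a good moment to reconcile it.

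### The only pain score taken before any allocated treatment is not used as a covariate in the primary 24h comparison and is not listed as a baseline characteristic

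*SAP*

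**What the plan says.** The outcome section of the SAP states: "The primary outcome will be the absolute VAS pain score 24h after surgery". *Primary analysis* describes the target as "Difference in absolute pain score 24h after surgery, assessed by 100mm visual analogue score (VAS), under the ITT principle [10". It then names a repeated-measures ANOVA of VAS before versus after stimulation or sham, with Tukey-Kramer post hoc tests. No covariate appears there or in any later model.

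*General analysis principles* nevertheless assumes that covariates exist: "Missing data for baseline covariates to be included in the analysis model will be accounted for using mean imputation for continuous variables", with a missing-indicator rule for categorical ones.

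Sessions take place both before and after surgery. In the secondary analysis by pain intensity, changes in VAS are "compared before and after the period of stimulation in each group before and after surgery". A VAS before the preoperative session is therefore required by analyses already planned.

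The *Baseline characteristics* list and dummy Table 1 include the GAD-7, the Amsterdam anxiety score, CRP and preoperative opioids, but no pain score. The only preoperative pain row is "VAS before surgery" in Table 4. It sits under secondary outcomes, in a table with treatment-effect and p-value columns.

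**The concern.** The reading before the first session is the only one that no allocated session can have influenced, so it is the natural baseline for the primary outcome. If it predicts pain at 24h, leaving it out keeps explainable variation in the error term, and the confidence interval is wider than it need be.

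The imputation rule for unnamed covariates is a gap within the SAP itself. Adjustment is foreseen but not specified, so the choice of covariates could be made after the data are seen.

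The Table 4 row needs correcting on either reading. If it is the post-session value, treatment may already have affected it and it cannot show baseline balance. If it is the pre-session value, the table provides for a treatment effect and p-value on a variable measured before treatment.

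**Working it through.** **Inputs from the SAP (sample size section):** means 34 and 23 mm, so a difference of 34 − 23 = 11 mm; SD of the outcome 12 mm; 90% power; "significant at the 1% level"; 72 evaluable patients, 36 per arm at 1:1. *General analysis principles* gives a different level: "For all analyses, a significance level of 5% will be used". Both levels are shown below.

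**Assumption:** rho, the correlation of the pre-first-session VAS with the 24h VAS, is not in the SAP. The range 0 to 0.6 is used.

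**Step 1. Reproduce the SAP's figure** ("72 patients are required to have a 90% chance of detecting"). By the normal approximation, two-sided 1%:

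n per arm = 2 × (2.576 + 1.282)² × 12² / 11² = 35.4, rounded up to 36, so 72 in total.

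This matches. The design rests on the unadjusted SD and takes no credit for a covariate. With the noncentral t distribution, used from here on, 36 per arm gives 88.9% power at 1%.

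**Step 2. Effect of adjustment.** ANCOVA residual SD = 12 × √(1 − rho²). Standard error of the difference = residual SD × √(2/36). The 95% half-width is the standard error times the t quantile (1.995 on 69 df). For rho 0.5: residual SD = 12 × √0.75 = 10.39 mm; SE = 10.39 × 0.2357 = 2.449 mm; half-width = 1.995 × 2.449 = 4.89 mm.

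| Analysis | Residual SD (mm) | Power at 1% | Power at 5% | 95% half-width (mm) |
|---|---|---|---|---|
| Unadjusted | 12.00 | 88.9% | 97.0% | 5.64 |
| ANCOVA, rho 0 | 12.00 | 88.9% | 97.0% | 5.64 |
| rho 0.2 | 11.76 | 90.3% | 97.5% | 5.53 |
| rho 0.3 | 11.45 | 92.0% | 98.0% | 5.38 |
| rho 0.5 | 10.39 | 96.5% | 99.3% | 4.89 |
| rho 0.6 | 9.60 | 98.5% | 99.8% | 4.51 |

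At rho 0, the lost degree of freedom moves power at 1% from 88.89% to 88.86%.

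**Step 3. Effect of a chance imbalance.** Assume the baseline VAS also has an SD of 12 mm. One standard error of imbalance is then 12 × √(2/36) = 2.83 mm. It would be expected to shift the unadjusted 24h difference by rho × 2.83: 0.85 mm at rho 0.3, 1.41 mm at 0.5 and 1.70 mm at 0.6, against a target of 11 mm.

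**The case against.** The strongest reply is that this is a choice about efficiency and not an invalid analysis. Randomisation makes the unadjusted comparison unbiased, and the sample size was built on the unadjusted SD. That stands. A reader might infer from the missing covariate that the primary result would be biased or the trial underpowered, and the document supports neither.

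A reader might also infer that an imbalance in starting pain could not be seen at all. That goes too far. Table 4 shows a preoperative VAS by arm, and a secondary analysis groups patients by pain intensity before the intervention. What remains is that the Table 4 row is unlabelled and treated as an outcome, and that the strata do not enter the primary comparison.

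The gain is also uncertain. Pain before surgery and pain 24h after it may have different causes, so a low rho cannot be excluded. At rho 0.2, power at 1% rises only from 88.9% to 90.3%. At the 5% level power is already 97.0%, so there the benefit is mainly a narrower interval. This also stands, and it is why the table starts at rho 0 and shows both levels.

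Finally, the repeated-measures ANOVA does use readings taken before a session. The SAP does not say which ones enter, and a before-versus-after contrast is not covariate adjustment of the 24h score. One might go on to charge the SAP with a less efficient change-from-baseline contrast, but it does not clearly specify one, so no figure for that is claimed here. Which contrast is primary is a separate question.

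**Conclusion.** The point holds as a matter of precision and specification. A pre-treatment VAS is implied by the planned analyses, the SAP anticipates baseline covariates without naming any, and neither the primary comparison nor Table 1 uses this reading. Baseline balance is not clearly shown, because the one preoperative row does not say which reading it holds.

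Under the SAP's own effect, SD and evaluable numbers, adjustment adds between nothing (rho 0) and 9.6 percentage points (98.5 − 88.9, rho 0.6) to power at 1%. At 5% the gain is at most 2.8 points (99.8 − 97.0). The half-width narrows by 0.26 mm at rho 0.3 and 0.75 mm at rho 0.5. The gain is small for rho of 0.3 or less and material from about 0.5. All of this rests on an assumed rho. The loss if rho is zero is negligible, so the change is worth making whatever its value turns out to be.

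**What to change.** 1. In *Primary analysis*, state that 24h VAS is compared between arms by ANCOVA, with arm and the VAS recorded before the first preoperative session (continuous) as covariate. Report the adjusted difference and its confidence interval in Table 4.
2. State that the imputation rule in *General analysis principles* applies if that baseline VAS is missing. This gives the rule a named covariate.
3. Add the pre-first-session VAS to the *Baseline characteristics* list and to Table 1.
4. Label the preoperative VAS row in Table 4 as pre- or post-session. If it is the pre-session value, give no treatment effect or p-value for it.

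The cost is one sentence in the analysis section, one line in the baseline list, one row in Table 1, a clearer label in Table 4, and one degree of freedom. No new data are needed. The change should be made before the outcome data are examined by arm.
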